#### **4.1 Screening/Baseline Visit procedures**

##### **Gait Biomechanics Assessment**

Subjects will walk forward along a 6m (~20 ft) walkway at a comfortable, self-selected “fast” speed while biomechanical data are collected. At least 5 practice trials will be performed during the familiarization session (Session 1) to determine the average preferred speed and ensure subjects can consistently strike a force plate mounted in the walkway with the test limb without noticeably altering their gait (i.e. “aiming” for the force plate). Gait speed will be monitored via an infrared timing system to ensure each trial is within  $\pm 10\%$  of the preferred speed. Kinematics (knee motion patterns), kinetics (knee joint moments and ground reaction forces) and lower extremity muscle activity (quadriceps and hamstrings EMG) will be sampled during each trial. Subjects will perform 5 valid trials from which gait biomechanical variables will be averaged for statistical analysis.

EMG electrodes will be placed over the back (hamstrings muscles) and front (quadriceps muscles) of the thigh via adhesive interfaces. Electrode placement sites will be shaved, lightly abraded, and cleansed with isopropyl alcohol to improve adhesion to the skin and signal quality. Motion capture markers will be secured on the trunk and pelvis, and the thigh, shank, and foot segments via double-sided tape. All measurement hardware will be further secured via hypoallergenic tape.

##### **Quadriceps Function Assessment**

Subjects will be seated on a device used to measure muscle strength called an isokinetic dynamometer. Straps will be used to secure the torso, thigh, and lower leg to the device with the knee in 60° of flexion. The moveable arm of the dynamometer will be fixed in place. Two adhesive stimulating electrodes will be placed on the anterior thigh over the quadriceps muscle. Subjects will be asked to contract the quadriceps maximally and as quickly as possible by “kicking out” against the dynamometer in response to a visual (light) stimulus while torque data are sampled. An investigator will view the torque data in real time and apply an electrical stimulus to the quadriceps after the torque reaches a maximal plateau. This electrical stimulus will consist of a 10 pulse train, pulse duration of 0.6ms, delivered at a frequency of 100Hz, and an intensity of 125V. The electrical stimulator will be isolated from fluctuations in building’s electrical power supply via a stimulus isolation unit. These methods and stimulus characteristics replicate those of previous investigations conducted in healthy and pathological

 populations, including the recent investigations conducted in our laboratories noted above. Quadriceps AMI will be quantified via peak torque (PT), rate of torque development (RTD), and the central activation ratio (CAR) during these maximal contractions. Measuring the CAR involves applying an electrical stimulus to a maximally contracting muscle (superimposed burst) which activates all the muscle's motor units. The ratio of torque resulting from the superimposed burst to the maximal voluntary torque represents the level of inhibition. Subjects will perform at least 2 practice trials to become familiar and comfortable with these procedures. Three trials will then be recorded from which PT, RTD, and CAR will be averaged for statistical analyses.

### **Proprioception/Somatosensory Assessment**

Proprioceptive/Somatosensory function will be assessed via a partial weight-bearing joint repositioning task. Subjects will be positioned supine on a sliding platform that will be reclined 75° relative to the vertical (Figure 5, Appendix A). This platform will permit unrestricted knee motion, but will control extraneous factors that influence joint position sense assessment during weight-bearing such as postural sway and trunk position. Subjects will be blindfolded, and each trial will begin with the knee in full extension, and subjects will flex the knee to a prescribed angle (reference angle) by sliding the platform downward. This angle will be maintained for 5s after which the subject will return to full knee extension, and will then attempt to replicate the reference angle. The absolute difference between the reference angle and the reproduced angle will be calculated and averaged across 5 trials for statistical analyses. Knee joint angles will be assessed via an electrogoniometer placed over the knee and secured using hypoallergenic double-sided tape.

We will also measure vibratory perception threshold (VPT), a more clinically feasible assessment of somatosensory function. Deficits in VPT have been identified in individuals with knee pathologies and are associated with impulsive loading during gait. VPT is measured using a device called a biothesiometer which vibrates at varying amplitudes that are controlled by the investigator. VPT will be assessed by placing the biothesiometer on bony prominences at the medial and lateral femoral epicondyles, medial (tibial) and lateral (fibular) malleoli, and 1st metatarsophalangeal joint. The amplitude of the vibration will be increased gradually, and subjects will verbally indicate the point at which they consciously perceive the vibratory stimulus, and the corresponding amplitude will be recorded as VPT. Three trials will be performed at each site and averaged for statistical analysis.

### **Self-Report Surveys**

The International Knee Documentation Committee Subjective Knee Form (IKDC), Knee Injury and Osteoarthritis Outcome Score (KOOS), and Tegner Activity Scale self-report surveys will be used to document subjects' knee trauma history, current symptoms, and functional ability. The IKDC and KOOS have been demonstrated as valid indicators of knee function and clinical outcomes in individuals with knee pathologies, while the Tegner scale is a valid indicator of physical activity level in these individuals. These surveys will be administered electronically via Qualtrics.

## **4.2 Intervention/Treatment procedures**

### **Vibratory Interventions**

All interventions will be performed with subject standing on a WBV device in approximately 40° of knee flexion, but the WBV device will only be "on" for the WBV group. Subjects assigned to the WBV group will receive a vibratory stimulus (30Hz, 2g) applied for 1 minute. This exposure will be repeated 6 times with 2 minutes of rest between exposures. Subjects in the LMV group will receive an identical stimulus (30Hz, 2g) via a custom-built vibrator secured over the distal anterior thigh. We have previously

demonstrated that these interventions enhance quadriceps activity. Subjects in the Control group will perform these exact same procedures with the exception that no vibratory stimulus will be applied. All interventions will be conducted by a graduate research assistant, and the PI will be blinded to group assignment.

#### **4.3 Follow-up procedures (by visits)**

None

#### **4.4 Unscheduled visits**

None

#### **4.5 Subject Completion/ Withdrawal procedures**

Subject participation in the study will be complete when he/she has completed Session 3. Subjects will receive prorated monetary compensation at this time.

#### **4.6 Screen failure procedures**

All subjects will provide informed consent prior to engaging in the screening procedures. Potential subjects who complete the screening session but do not meet the inclusion criteria will be thanked for their time and excluded from further participation.

### **5 STUDY EVALUATIONS AND MEASUREMENTS (how measurements will be made)**

See 4.1 Screening/Baseline Visit procedures

#### **5.1 Safety Evaluations**

All data will be deidentified. Subjects will be identified only by a subject ID# to which their personal information will not be linked. Deidentified data files (e.g. gait biomechanics data trials) will be stored and backed up in numerous password-protected locations including computers in the Neuromuscular Research Laboratory, external hard drives, and the UNC-CH Research Computing Mass Storage System.

[name] from the UNC-Chapel Hill Department of Orthopaedics will serve as the Research Monitor for this investigation. [name] possesses both the research ethics and medical expertise necessary to carry out this role. The PI will provide the Research Monitor a summary report during each quarter of the funding period detailing the information that is necessary for [name] to perform his duties. These duties will include ensuring subjects meet the enrollment criteria, verifying the informed consent process for each subject, and monitoring adverse events. A detailed description of the Research Monitor's duties and authorities (i.e. conditions under which the Research Monitor can suspend research activities) has been uploaded in IRBIS.

Prior to analysis, the data will be screened for outliers (values more than 3 sd beyond the mean) and evaluated for normality via the Shapiro-Wilk test, visual inspection of the histograms, and evaluation of the ratios of the skewness and kurtosis statistics to their standard errors to ensure quality.

The 5-minute warm-up prior to testing is designed to reduce the risk of muscle soreness and/or injury during testing. The electrical stimulator used for the Quadriceps Function Assessment will always be connected to a stimulus isolation unit to ensure that the subject is isolated from fluctuations in the building's power supply. Any safety concerns (i.e. musculoskeletal injury) would likely be recognized immediately during testing, but subjects will be instructed via the informed consent document that they should inform UNC Student Health Services or their personal physician in the event that they experience lingering issues after leaving the laboratory.

All members of the research team involved with data collection are certified in CPR and First Aid. These individuals will monitor subjects for adverse events during testing, and will refer any individuals who experience adverse events to the Stallings-Evans Sports Medicine Center (located in the building adjacent to Fetzer Hall where the Neuromuscular Research Laboratory is located), UNC Student Health Services, or Emergency Medical Services depending on the nature and severity of the adverse event.

## **6 STATISTICAL CONSIDERATION**

### **6.1 Primary Endpoint**

This pre-clinical trial will evaluate the acute effects of the interventions, thus the immediate post-test assessment will serve as the primary endpoint.

### **6.2 Statistical Methods**

**Specific Aim 1: To determine the effects of WBV and LMV on quadriceps function, proprioception, and gait biomechanics in individuals with ACLR.**

Analyses for Aim 1 will be performed using pre-post change scores for quadriceps function, proprioception, and gait biomechanics as dependent variables in separate statistical models. Mean change scores will be compared across groups (WBV, LMV, and Control) via one-way analysis of covariance (ANCOVA). Dunnett's procedure will be used to evaluate each the least-squares means for each of the intervention arms (WBV and LMV) versus control in a relatively powerful manner while controlling the overall significance level at two-sided 0.05. The corresponding pre-test values for each dependent variable will be managed as a covariate in these models to increase precision of the treatment effects, as well as to account any random imbalances among the groups with respect to these pre-scores. Other covariates would include variables with random imbalances across the groups measured at the pre-test.

The number of individuals who display HST prior to and following the intervention (or control) will be compared via McNemar's test. This analysis produces a  $\chi^2$  statistic for paired samples (i.e., the proportion with HST at pre-test vs. post-test, separately for each group).

**Specific Aim 2: To compare the effects of WBV and LMV on quadriceps function, proprioception, and gait biomechanics in individuals with ACLR.**

Aim 2 will be evaluated using the statistical models described above for Aim 1, but with focus on the statistical contrast of WBV versus LMV. Specifically, the pre-post change scores for each dependent

variable, adjusted for covariates, will be tested for the pairwise comparison of WBV versus LMV at the two-sided 0.05 significance level.

**Specific Aim 3: To identify factors that predict the effects of LMV and WBV on quadriceps function, proprioception, and gait biomechanics in individuals with ACLR.**

Aim 3 will be evaluated using multiple regression models. Pre-post change scores for each dependent variable will be included only for the WBV and LMV groups. We will then calculate simple correlations between these change scores and the pre-test values separately for quadriceps function, proprioception, and the KOOS. We hypothesize that individuals with greater quadriceps dysfunction and proprioceptive deficits combined with lower KOOS scores (i.e. greater pain, symptoms, etc.) will display greater improvements. Separately for each dependent variable, these variables will then be placed into a stepwise multiple regression model (starting with a forward selection step). In this way, the variable with the strongest relationship with the change score will be entered first, followed by the next strongest (after adjusting for the first), etc. The model selection will stop when no additional variables are identified to enter to leave the model at the 0.10 significance level. This less conservative significance level is selected to cast a wide net to include relevant candidate terms. Next, we will examine each of these terms, one-at-a-time, as an independent variable in another regression model where the change score is the dependent variable; an indicator term for the intervention (WBV vs. LMV) will also be included as an explanatory variable, as well as the interaction between the intervention indicator and the candidate term. The initial focus will be on the significance of the interaction term, as this will determine whether the effect of the candidate term is homogeneous (reflected by non-significance of the interaction at the 0.05 level) across the interventions, or not. If the test is non-significant, the interaction term will be removed and the model refitted; the candidate term is then assessed from this model regarding its ability to predict the homogeneous effect of LMV and WBV on the corresponding dependent variable. If the interaction test is instead statistically significant, then the interaction term is retained in the model, and statistical contrasts will be constructed to estimate and test the separate effects of the candidate term by intervention group.

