### **6.3 Sample Size and Power**

Quadriceps function is the primary outcome for this investigation, as it is the critical factor in controlling impulsive knee joint loading linked to development of post-traumatic knee OA. We conducted *a priori* power analyses using data from our preliminary investigation involving these same vibratory stimuli following experimental knee joint effusion. Pre-post change scores were calculated as described above in the statistical methods for Specific Aim 1, and effect size indices were calculated for one-way ANCOVA using pre-test scores as the covariate. These analyses indicate that a sample of 45-63 subjects (15-21 per group) would provide statistical power of 0.80 for  $\alpha = 0.05$  to identify significant overall ANCOVA models for CAR ( $f = 0.48$ ) and peak torque ( $f = 0.41$ ), where  $f$  is the effect size calculated as the square root of the ratio of the between-group sum of squares and the error sum of squares. Further, these preliminary data generated the pairwise effect sizes presented in the table below calculated using the following equation:

$$\text{Effect Size} = \frac{[\Delta\text{WBV} \text{ (or } \Delta\text{LMV} \text{ )} - \Delta\text{Control}]}{\text{Pooled Standard Deviation}}$$

Effect Sizes for *Post Hoc* Group Comparisons of Pre-Post Change Scores

Quadriceps Function Variable	WBV vs. Control	LMV vs. Control	LMV vs. WBV
CAR	0.84	0.78	0.36
Peak Torque	0.98	0.70	0.35

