Statistical power for the effect sizes given in Table 2 was calculated for one-tailed independent t-tests. These estimates indicate that a sample of 39-78 subjects (13-26 per group) would provide statistical power of 0.80 for  $\alpha = 0.05$  to evaluate pairwise comparisons between the Control group and each vibratory intervention (i.e. Aim 1). In contrast, 194 subjects (97 per group) would be necessary to provide adequate power to identify the relatively small effect sizes for comparing the two vibratory interventions (i.e. Aim 2). The associated mean differences in CAR between WBV and Control and between LMV and Control were 8.26% and 5.86%, respectively, while the difference between LMV and WBV was only 0.68%. Similarly, the associated mean differences in peak torque between WBV and Control and between LMV and Control were 0.29 N/kg and 0.20 N/kg respectively, while the difference between LMV and WBV was only 0.04 N/kg. These data suggest that the small mean differences in the dependent variables between WBV and LMV, even when powered sufficiently, are not likely clinically or physiologically relevant. Therefore, we will recruit a sample of 75 individuals (25 per group) to address the proposed specific aims. This sample size will provide adequate power to demonstrate similar improvements in quadriceps function with WBV and LMV.

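### Section 6.2 leaves the form of Dunnett's procedure open; specifying step-down Dunnett would raise the chance of showing the second vibration arm better than Control at the same overall two-sided 0.05

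*Combined protocol and SAP*

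**What the plan says.** Section 6.2 (Specific Aim 1) compares mean change scores across WBV, LMV and Control by one-way ANCOVA, with the pre-test value as covariate and a separate model for each dependent variable. Dunnett's "procedure will be used to evaluate each the least-squares means for each of the intervention arms (WBV and LMV) versus control". Power is given as one reason for the choice, and the other is "controlling the overall significance level at two-sided 0.05". No form of the procedure is named, neither single-step nor step-down, and no confidence intervals are promised.

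Section 6.3 makes quadriceps function the primary outcome and tabulates pairwise effect sizes, in the order WBV vs Control, LMV vs Control, LMV vs WBV: "CAR 0.84 0.78 0.36" and "Peak Torque 0.98 0.70 0.35". Power for these "was calculated for one-tailed independent t-tests". On that basis, "These estimates indicate that a sample of 39-78 subjects (13-26 per group) would provide statistical power of 0.80" for the comparisons with Control. The trial takes 25 per group. No power is given for the two-sided Dunnett analysis that section 6.2 plans.

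**The concern.** Named without qualification, Dunnett's procedure is normally read and programmed as the single-step version, which applies one critical value to both comparisons. With only two comparisons, that is stricter than the stated error rate requires. Once the comparison with the larger |t| has been rejected, at most one true null hypothesis can remain, and it needs no further multiplicity adjustment.

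The cost falls on whichever arm has the smaller observed effect. On section 6.3's peak-torque figures that is more often LMV (0.70 against 0.98 for WBV). It also lowers the chance that both arms are shown better than Control. That result bears on the closing statement of section 6.3, which expects the trial to show that WBV and LMV improve quadriceps function similarly. Because the two forms can disagree about the second arm, leaving the form unstated also leaves a choice open until analysis.

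**Working it through.** **Inputs.** 25 per group (section 6.3). Overall two-sided 0.05 (section 6.2). Error df = 75 − 3 groups − 1 covariate = 71. Effect sizes from the section 6.3 table: peak torque 0.98 (WBV) and 0.70 (LMV); CAR 0.84 and 0.78. With equal groups sharing one Control, the two comparisons have correlation 0.5.

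**Step 1: the plan's own figure.** For a one-tailed test at 0.05 with power 0.80, n per group = 2(1.645 + 0.842)²/d² ≈ 12.37/d².
- d = 0.98: 12.37/0.960 = 12.9, so 13 (14 by the t distribution).
- d = 0.70: 12.37/0.49 = 25.2, so 26 (26 by the t distribution).

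The stated 13 to 26 per group reproduces.

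**Step 2: critical values on 71 df.** Two-sided Dunnett for two comparisons, correlation 0.5: 2.257. Unadjusted two-sided 0.05: 1.994. With 72 df (no covariate) they are 2.256 and 1.993.

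**Step 3: the two rules.**
- Single-step: reject each comparison if its |t| > 2.257.
- Step-down: compare the larger |t| with 2.257. If it is rejected, compare the other with 1.994; otherwise stop.

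**Step 4: error control of step-down.** If both nulls are true, any rejection needs the larger |t| to exceed 2.257, which has probability 0.05. If one null is true, rejecting it needs its own |t| to exceed at least 1.994, which has probability at most 0.05. Simulated family-wise error (4 million trials per case): 0.050 with both nulls true; 0.045 with LMV null and WBV 0.98; 0.050 with LMV null and WBV very large; 0.040 with WBV null and LMV 0.70.

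**Step 5: power at 25 per group.** The expected t is about d × √(25/2) = 3.536d, so 3.46 and 2.47 for peak torque, and 2.97 and 2.76 for CAR. Results from 4 million simulated trials:

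| | Single-step | Step-down |
|---|---|---|
| Peak torque, WBV | 0.884 | 0.897 |
| Peak torque, LMV | 0.588 | 0.673 |
| Peak torque, both | 0.561 | 0.659 |
| CAR, WBV | 0.761 | 0.799 |
| CAR, LMV | 0.691 | 0.748 |
| CAR, both | 0.589 | 0.685 |

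**Step 6: what does not change.** The chance of at least one rejection is WBV + LMV − both. For peak torque: 0.884 + 0.588 − 0.561 = 0.911 under single-step, and 0.897 + 0.673 − 0.659 = 0.911 under step-down. For CAR it is about 0.862 under both.

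**Step 7: where the gain lies.** Step-down only ever adds the second rejection. It does so in 0.659 − 0.561 = 9.8% of trials for peak torque and 0.685 − 0.589 = 9.6% for CAR. In each of these the second |t| lies between 1.994 and 2.257, so its single-step simultaneous interval includes zero.

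**Step 8: distance from 0.80 for LMV peak torque.** The one-tailed unadjusted t-test used for sizing gives 0.787 at 25 per group. The unadjusted two-sided test on 71 df gives 0.685, which is the ceiling for any two-sided method here. Step-down gives 0.673 and single-step 0.588.

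**The case against.** **The plan is valid.** Dunnett's procedure is standard, prespecified and controls the level claimed. This stands. A reader might infer that section 6.2 contains an error, or that it commits to the single-step form. The text supports neither: single-step is only the usual reading of an unqualified name.

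**Tests and intervals would disagree.** Every rejection gained comes with a single-step simultaneous interval that covers no effect. For a proof-of-concept study meant to inform a larger trial, keeping tests and intervals in agreement is a respectable reason to stay with single-step. This also stands, and the downside has to be stated. It does not defeat the suggestion, because section 6.2 describes tests, asks for power and promises no intervals.

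**The gain is limited.** The LMV peak-torque gain is the largest of the four per-arm gains; the others are about 0.01, 0.04 and 0.06. A reader might infer that step-down repairs the power of the LMV comparison. It does not. Most of the fall from 0.787 to 0.588 would be recovered only by reconciling the one-tailed sizing in section 6.3 with the two-sided analysis in section 6.2.

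**The power levels rest on soft inputs.** Section 6.3 divides by a pooled SD, and the calculation treats that as one common ANCOVA error SD. If the covariate removes further variance, the levels rise: with an assumed baseline–change correlation of 0.3 or 0.5, LMV peak-torque power goes from 0.63 to 0.72 or from 0.73 to 0.80. The gain stays near 0.08. For CAR the inputs do not reconcile. The implied SDs are 8.26/0.84 = 9.8 and 5.86/0.78 = 7.5. The two differences from Control imply 8.26 − 5.86 = 2.40 between WBV and LMV, against a stated 0.68. The effect sizes differ by 0.06, against a tabled 0.36. The CAR powers are therefore indicative only.

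**LMV is not favoured by the aims.** Section 1.3 lists practical advantages of LMV, and a reader might infer that LMV is the arm the sponsor mainly wants to establish. The aims treat WBV and LMV symmetrically, so the case for step-down rests on the second-ranked arm, whichever it is.

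**Conclusion.** This is a cheap improvement and not an error. Step-down Dunnett meets both of section 6.2's stated purposes, power and overall two-sided 0.05, at least as well as single-step: it rejects everything single-step rejects and sometimes more. The benefit is confined to the second comparison, and the downside is the disagreement between test and interval described above.

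The absolute power levels assume that the tabled effects are true, that they sit on the ANCOVA error SD scale with one common SD, and that 25 per group have complete data. The documents state no dropout allowance. The gain is more robust than the levels. Error control holds within each dependent variable only; step-down does nothing about multiplicity across quadriceps, proprioception and gait outcomes. Under these assumptions LMV peak-torque power remains below the 0.80 target, and that shortfall is a separate matter for section 6.3.

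**What to change.** In section 6.2, before any unblinded data are seen, replace the unqualified reference to Dunnett's procedure with text to this effect:

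*The two comparisons with Control will be tested by step-down Dunnett within each dependent variable. The larger |t| is compared with the two-sided 0.05 Dunnett critical value. If it is rejected, the other is compared with the unadjusted two-sided 0.05 critical value; if not, neither is rejected. Step-down adjusted p-values will be reported: the Dunnett p-value for the larger |t|, and for the other the greater of that value and its own unadjusted two-sided p-value. The step-down test decides significance. Single-step simultaneous intervals are descriptive and may include zero for a comparison declared significant.*

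The cost is a few sentences and a small programming change, with no added subjects or data. If the investigators prefer tests and intervals that always agree, they should keep single-step and say so in section 6.2. Either way the form should be named.

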3. Knee Injury and Osteoarthritis Outcome Score (KOOS) self-report survey Pain subscale score > 53.1 and Symptom subscale score > 44.9
4. Cleared by physician to resume physical activity, and currently physical active at least 20 minutes 3x per week
5. Quadriceps central activation ratio < 95%

Exclusion Criteria

6. History of ACL graft rupture
7. History of neurological disorder
8. History of musculoskeletal injury to either leg within the 6 months prior to participation
9. Pregnant or planning to become pregnant

---

Number Of Subjects	75
Study Duration	Each subject's participation will last approximately 3 hours and 45 minutes over approximately 2 weeks.  The entire study is expected to last 3 years.
Study Phases	(1) Screening : screening for eligibility and obtaining consent and (2) Intervention : study intervention/experimental treatment. Phase 2 will involve 2 testing sessions separated by approximately 1 week.
Screening	
Study Treatment	
Follow-Up	
Efficacy Evaluations	
 
1. Gait biomechanics (vertical ground reaction force linear and instantaneous loading rates, peak internal knee extension moment, peak internal knee valgus moment)
 
2. Somatosensory function (knee joint position sense error)
 
3. Quadriceps function (isometric peak torque)
 

Statistical And Analytic Plan	Pre-Post change scores for each of the primary outcomes will be compared between groups via one-way ANCOVA
DATA AND SAFETY MONITORING PLAN	[name] from the UNC-Chapel Hill Department of Orthopaedics will serve as the Research Monitor for this investigation. The PI will provide the Research Monitor a summary report during each quarter of the funding period that details information detailing enrollment, verification of informed consent, and adverse event documentation. The Research Monitor's primary responsibilities relate to the proper conduct of the investigation and the welfare of the subjects who are involved. As such, [name] will have the authority to suspend research associated with the project in the event of violations of study protocol.

---

[figure not shown]

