## **4 STUDY PROCEDURES (what will be done)**

Subjects will report to the UNC Neuromuscular Research Laboratory for three separate sessions. During Session 1, subjects will complete the approved informed consent document, as well as the Self-Report Surveys, Gait Biomechanics Assessment, and Quadriceps Function Assessment described below. These procedures will be used to determine if subjects meet the inclusion criteria, familiarize the subject with the testing procedures, and establish parameters necessary for the subsequent testing sessions to expedite data collection. Upon reporting to the laboratory for Session 2, subjects will perform a 5 minute warm up on a stationary cycle ergometer at a self-selected pace to reduce the likelihood of injury. They will then be fitted with motion capture markers and electromyography (EMG) electrodes followed by the Gait Biomechanics and Quadriceps Function assessments. They will then perform the respective intervention to which they have been assigned, followed by post-test measures of the aforementioned assessments. Procedures for Session 3 will be identical with the exception that the Proprioception/Sensory Assessment described below will be performed prior to and following the interventions. Sessions 2 and 3 will be separated by 1-week washout periods, and the order of these sessions will be counterbalanced.

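### The ANCOVA's only prespecified covariate is the pre-test value; the Session 1 quadriceps baseline, already collected, is given no role in the analysis

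*Combined protocol and SAP*

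**What the plan says.** Section 6.2, Specific Aim 1, compares pre-post change scores across the three groups by ANCOVA and names one covariate in advance: "The corresponding pre-test values for each dependent variable will be managed as a covariate in these models". The stated reasons are precision and correction of chance imbalance. The next sentence leaves the remaining covariates open: "Other covariates would include variables with random imbalances across the groups measured at the pre-test". Aim 2 uses the same models. Section 6.3 names quadriceps function as the primary outcome and bases its effect sizes on the pre-test covariate alone.

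Section 4 has each subject complete, in Session 1, the consent document "as well as the Self-Report Surveys, Gait Biomechanics Assessment, and Quadriceps Function Assessment described below". On purpose, it says: "These procedures will be used to determine if subjects meet the inclusion criteria, familiarize the subject with the testing procedures"; Session 1 also sets parameters for the later visits. Under Quadriceps Function Assessment, section 4.1 says: "Three trials will then be recorded from which PT, RTD, and CAR will be averaged for statistical analyses". No section gives the Session 1 values a place in the analysis beyond eligibility.

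In Session 2, gait and quadriceps function are measured, the intervention is given, "followed by post-test measures of the aforementioned assessments". Then: "Procedures for Session 3 will be identical with the exception that the Proprioception/Sensory Assessment described below will be performed" before and after the intervention. Read literally, the quadriceps pre/post pair is repeated in Session 3. Neither section 6.1 nor section 6.2 says which pair is analysed or how two pairs would be combined.

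**The concern.** An enrolled subject has at least two pre-intervention readings of PT, RTD and CAR, taken on different days. The model is committed to one of them. A mean of three trials on one day contains trial-to-trial and day-to-day noise, so a reading from another day can explain some of the variation that the same-day pre-test leaves. Session 1 precedes all vibration, so adjusting for it is legitimate in a randomised comparison.

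What is at stake is precision on the primary outcome, in a trial of 25 per group. The route the plan does offer for extra covariates selects on observed imbalance. That choice is made after the data are seen, does not clearly reach Session 1, and is a poor guide to precision, which depends on how well a covariate predicts the outcome.

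**Working it through.** **Inputs from the documents.** 75 subjects, 25 per group (section 6.3). Pairwise effects against Control: CAR 0.84 (WBV) and 0.78 (LMV); PT 0.98 (WBV) and 0.70 (LMV). Analysis by Dunnett's procedure at overall two-sided 0.05 (section 6.2). CAR entry limit: "Quadriceps central activation ratio < 95"% (synopsis).

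**Assumptions.** The documents give no pre-post or between-day correlation. Let rs be the same-day pre-post correlation and rb the correlation of the Session 1 value with both the pre-test and the post-test. The tabulated effects are taken to be in units of the residual SD of the one-covariate ANCOVA. If they use the raw change-score SD, starting power is higher. No dropout is applied.

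**Step 1: the plan's own figures.** Overall F test, three groups, noncentrality f²N, α = 0.05: f = 0.48 gives 15 per group (power 0.80 at N = 45) and f = 0.41 gives 21 per group (power 0.82 at N = 63). This matches the stated 45–63. One-tailed pairwise: d = 0.98 gives 13 (normal approximation; 14 by t) and d = 0.70 gives 26, matching 13–26 per group. For LMV versus WBV, d = 0.36 gives 97 per group, also a match.

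**Step 2: power of the planned analysis.** Two-sided Dunnett, two comparisons, 71 error df, critical value 2.257, noncentrality d√(25/2):

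- d = 0.98: 0.88
- d = 0.84: 0.76
- d = 0.78: 0.69
- d = 0.70: 0.59

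**Step 3: adding Session 1.** With the pre-test in the model, the residual variance is the same for the change score as for the post-test, namely 1 − rs². With both covariates it is 1 − (rs² + rb² − 2·rs·rb²)/(1 − rb²). The variance ratio VR is the second divided by the first. Example, rs = 0.9 and rb = 0.8: (0.81 + 0.64 − 1.152)/0.36 = 0.828; 1 − 0.828 = 0.172; 0.172/0.19 = 0.906. Power replaces d by d/√VR, with 70 error df and critical value 2.258.

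| rs / rb | VR | 25/VR per group | Power, d = 0.70 |
|---|---|---|---|
| 0.95 / 0.6 | 0.986 | 25.4 | 0.59 |
| 0.9 / 0.6 | 0.970 | 25.8 | 0.60 |
| 0.9 / 0.7 | 0.949 | 26.3 | 0.61 |
| 0.8 / 0.6 | 0.938 | 26.7 | 0.62 |
| 0.9 / 0.8 | 0.906 | 27.6 | 0.63 |
| 0.8 / 0.7 | 0.893 | 28.0 | 0.64 |
| 0.8 / 0.8 | 0.802 | 31.2 | 0.69 |
| 0.9 / 0.9 | 0.776 | 32.2 | 0.71 |

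Where the same-day pre-test predicts better (first six rows), residual variance falls by 1–11%. Where the two are equally informative, VR = (1 + 2r)/(1 + r)², which runs from 0.889 at r = 0.5 to 0.776 at r = 0.9; that is 11–22% less, and about 20% at r = 0.8.

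**Step 4: truncation of CAR.** Selecting on Session 1 CAR narrows its range. In simulation, if the rule removes the top 25% or 50% of values, VR moves from 0.802 to 0.841 or 0.867 (0.8/0.8), and from 0.906 to 0.927 or 0.939 (0.9/0.8). Eligibility sets no cut-off on PT or RTD.

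**Step 5: cost if Session 1 is uninformative.** Allowing for chance covariate imbalance, a second covariate multiplies the expected variance of a contrast by 70/69 = 1.0145. At d = 0.70 a useless covariate costs about 0.7 percentage points of power. Break-even is a partial correlation of √(1 − 69/70) = 0.12. The 0.95/0.6 row sits there: 0.986 × 1.0145 = 1.00, no net gain.

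**Step 6: if Sessions 2 and 3 were averaged.** Under the same correlation structure, averaging both pre/post pairs weakens the benefit: VR goes from 0.80 to 0.86 (0.8/0.8) and from 0.91 to 0.93 (0.9/0.8). The choice of pair therefore has to be settled in the same edit.

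**The case against.** The strongest reply is that nothing is broken. The same-session pre-test is the natural baseline for an acute, immediate post-test endpoint (section 6.1). The trial was sized on that covariate, the stated sample sizes reproduce, and Session 1 is a screening and familiarisation visit. All of this stands, and it limits the point to efficiency.

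Four stronger readings are tempting and are not supported.

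- A reader might infer that a noisy single baseline biases the treatment comparison. Under randomisation, measurement error in a baseline covariate costs precision and does not bias the contrast.
- A reader might infer that the model allows no other covariate. Section 6.2 does allow others, but chosen by observed imbalance and without naming Session 1. The accurate statement is that the pre-test is the only prespecified one.
- A reader might infer that every outcome would gain. Proprioception is not measured in Session 1. For gait, section 4 lists the assessment in Session 1, but section 4.1 describes practice trials there to set walking speed, and section 4 mentions markers and EMG electrodes only from Session 2.
- A reader might infer that the gain is free, or that it repairs the power shortfall. It costs a degree of freedom. No case examined brings d = 0.70 to 0.80. The 0.59 arises because section 6.3 uses one-tailed t-tests while section 6.2 plans a two-sided Dunnett test, which is a separate matter.

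**Conclusion.** The point holds as an efficiency improvement for PT, RTD and CAR. The planned ANCOVA is valid, but it leaves out a pre-treatment reading of the primary outcome that will already exist, while leaving further covariates to a data-driven choice.

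The size is conditional. At the low end the benefit is negligible. The best case requires Session 1, a familiarisation visit on another day, to predict the post-test as well as the same-day pre-test does. For CAR the gain is smaller at any given pair of correlations. All of these figures rest on assumed correlations and on reading the tabulated effects in residual-SD units. The possible loss is under one percentage point of power, against a possible gain of roughly ten, which favours making the change.

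**What to change.** In section 6.2, for Aims 1 and 2:

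- Prespecify the Session 1 value of the same measure as a second covariate in the ANCOVA for PT, RTD and CAR, alongside the pre-test from the analysed session.
- Delete the clause that selects covariates by observed imbalance.
- State which session's quadriceps pre/post pair is analysed, or how two pairs are combined, and reconcile this with the description of Session 3 in section 4.
- Extend the second covariate to gait only if the full gait variables are in fact recorded in Session 1. Leave the proprioception models as they are.
- Describe the expected gain as depending on the between-session correlations. If the investigators hold such correlations from earlier work, they can be used to place the trial within the range above.

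The cost is a few sentences in the SAP and one error degree of freedom per model. No added visit, measurement or subject is needed. The mismatch between one-tailed powering and two-sided testing needs its own correction.
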